## The main contributions of this study are:

To the best of the authors' knowledge, this is the first study in Iraq that highlighted the surviving victims of ISIS with SCIs.

The preparation of a home-based rehabilitation program (HBRP) that lasted for six months and that was compatible with the participants' living and environmental conditions as an alternative solution for conditions after the war also, at the time of the COVID-19 pandemic when everything was under the closure.

Assessing the effectiveness of rehabilitation on some anthropometric and physical variables in participants with SCI following participants' stopping of rehabilitation for (4-5) years after SCI.

## The study raises two questions

Does the home-based rehabilitation program (HBRP) affect people with spinal cord injury through interruption of rehabilitation for 4-5 years?

Is the HBRP effects on variables such as body composition (Weight, BMI); Anthropometric Measures, and Muscle strength?

#### Methods

This voluntary controlled trial included 18 volunteers split into three groups: 13 people with Spinal Cord Injury (SCI) their injuries time since (53.4-55) months. They joined voluntarily into Two groups, eight in the experimental group (Exp.) and Five in the first control (1st Con.); while five were healthy individuals in the second control (2nd Con.); all around (21.2) years old on average. As a first procedure, detailed interviews were conducted with each participant at the beginning of the study to gather information about their physical, psychological, and social well-being. This information helped the authors create personalized rehabilitation plans for each participant to ensure their

participation in the study for the entire 6 months period. Through our study objectives, the authors used body composition such as height, weight, BMI and some anthropometric measurements for body parts circumferences by using tape measurements, similar to a previous study by Akita et al. Also, muscle strength tests were performed on participants' lower and upper extremities, head, and trunk to measure various movements. The 2nd control group completed their measurements and tests at college. Additionally, a clinical test using the American Spinal Injury Association scale (ASIA) was conducted on each participant to assess sensory feeling and voluntary movement potential on both sides of the body.

The physical tests were conducted using a handheld muscle tester called MicroFET2 to evaluate the strength of participants' lower extremities, head, and trunk by using unit measure kilogram (kg) 11. The Exp. group underwent a 6-month intensive rehabilitation program that involved whole-body exercises, including stretching, strength, endurance, and aerobic training, which was prepared based on previous studies 12. The program included five weekly sessions of (45-120) minutes, gradually increasing in intensity. It encompassed various exercises like bed exercises, rubber ball exercises for strength and balance, trunk flexibility exercises, crawling, rolling, ball-related movements, and exercises on parallel bars. Also, aerobic exercises targeted cardiorespiratory fitness. While weight exercises focused on the upper limbs, shoulders, chest, and back. Rest periods were personalized based on injury severity and overall health. The authors updated the exercises based on regular assessments every 3 months, tracking muscle strength and endurance. The authors created a contact link for coordination among medical, rehabilitative teams, and participants, families, overcoming some challenges within the Iraqi healthcare system.

To address complex complications like bed sores, renal infections, and muscle atrophy, the authors followed the method of psychological support. This method aimed to stimulate patients, willpower, encouraging them to overcome complications and emphasizing the benefits of rehabilitation for improved overall health and independence, by made WhatsApp group was created to facilitate information sharing and provide visual evidence of successful cases, inspiring and encouraging participants. Furthermore, the participant weight and BMI were monitored due to the potential impact of factors such as limited movement and hormonal changes on weight fluctuations, as recommended in previous studies.

The study highlights the participants the participants fidelity to treatment, as evidenced by positive outcomes and sustained progress beyond the conclusion of the therapeutic experiment. The participants demonstrated loyalty through ongoing communication with the main author, seeking feedback on their rehabilitation stages who reach it. Notably, some participants achieved the significant milestone of walking by standard walker with the assistive device Knee-Ankle-Foot-Orthosis (KAFO).

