# Feasibility of Home-Based Rehabilitation on Body Composition, some Anthropometric Measures and Muscular Strength after interruption 4-5 years of Spinal Cord Injury: Serial Cases Study on ISIS War Survivors in Iraq

## **Summary**

Background: The war in Mosul wrecked hospitals and rehab centers, leaving a gap in rehabilitation services. This resulted in a need for alternative solutions for rehabilitation. Objectives: This study aims to create a home-based rehabilitation program (HBRP) that fits the participant; surroundings, and also detect and evaluate how effective it is in improving body composition, some anthropometric measurements, and muscle strength after a (4-5) year break in rehabilitation.

Methods: This voluntary controlled trial included 18 volunteers split into three groups: 13 people with Spinal Cord Injury (SCI) their injuries time since (53.4-55) months. They joined voluntarily into Two groups, Eight in the experimental group (Exp.) and Five in the first control (1st Con.); while Five were healthy individuals in the second control (2nd Con.); all around (21.2) years old on average. The HBRP focused on muscles and whole-body joints by using the basic equipment and exercises right at the patient's homes. The program consisted of five weekly sessions with a gradually increasing achievement time of (45-120) minutes per session, participants were given rest time between exercises based on their level and severity of injury. The assessment was every three months.

Innovatively, this study stands out by introducing an HBRP tailored for individuals with SCI after interruption sustained (4 - 5) years ago. This unique approach not only addresses the challenges posed by the interruption of previous rehabilitation efforts but also seeks to uncover the efficacy of rehabilitation in these specific circumstances.

Conclusions: The study concluded that HBRP affected positively the muscles morphologically and functionally despite a stop in rehabilitation for a long period of (4-5) years for individuals with SCI.

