## **Statistic Analyze**

The study used Two-way ANOVA repeated measures as a statistical analysis method, with effect size and improvement percentage (IP) as measures, and (IBM-SPSS statistics processor version 20) for data analysis. A statistical significance level of  $P \le 0.05$  (alpha) was used.

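### Non-randomised SCI groups (8 versus 5): the reported ANOVA does not identify the Exp versus 1st Con difference in change, and the Summary's causal conclusion goes beyond the design

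*Protocol*

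**What the plan says.** - **Group formation.** Protocol, Methods: "They joined voluntarily into Two groups, eight in the experimental group (Exp.) and Five in the first control (1st Con". The same section adds a third group: "while five were healthy individuals in the second control (2nd Con". Of that group it says: "The 2nd control group completed their measurements and tests at college". No randomisation, matching or baseline comparison is described. In the Combined protocol and SAP, the randomisation field (5.5) lists data elements and gives no allocation method.
- **Question.** Protocol, The study raises two questions: "Does the home-based rehabilitation program (HBRP) affect people with spinal cord injury through interruption of rehabilitation for 4-5 years".
- **Analysis.** Protocol, Statistic Analyze: "The study used Two-way ANOVA repeated measures as a statistical analysis method", "with effect size and improvement percentage (IP) as measures", at a 0.05 level. It names no factors, no effect of interest, no contrast and no confidence interval.
- **Timing.** Protocol, Summary: "The assessment was every three months". The programme lasted 6 months.
- **Conclusion.** Protocol, Summary: "The study concluded that HBRP affected positively the muscles morphologically and functionally despite a stop in rehabilitation". No qualification for the way the groups were formed appears in the visible text.

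**The concern.** The question is whether the programme changes outcomes in people with SCI. The comparison that bears on it is change in Exp against change in 1st Con. An omnibus ANOVA over three groups, one of them healthy, can be significant for reasons unrelated to that comparison. The text does not tell the reader which groups or which line of the ANOVA table carry the conclusion.

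Even the right contrast would compare people who were not randomised. The programme asks for five sessions a week of 45 to 120 minutes over 6 months, so motivation or residual function could plausibly be related to who ended up in it. A sentence that attributes the change to the programme claims more than such a comparison can show.

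**Working it through.** **No figure to reproduce.** The counts add up (8 + 5 = 13; 13 + 5 = 18). The documents give no power, target difference or SD from which 18 could be derived.

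**Inputs from the documents.** Group sizes 8, 5 and 5; level 0.05 (taken as two-sided); assessment every three months over 6 months.

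**Assumptions.** Assessments at 0, 3 and 6 months; equal correlation between times, 0.5 to 0.9; linear drift; no programme effect in steps 2 and 3. Drift is in SD of the 0-to-6-month change.

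**Step 1. What the Exp versus 1st Con contrast can deliver.**
- SE factor: √(1/8 + 1/5) = √0.325 = 0.570.
- Degrees of freedom 8 + 5 − 2 = 11; t(0.975) = 2.201.
- 95% CI half-width: 2.201 × 0.570 = 1.25 SD of change.
- Power from the noncentral t: 13% at a true difference of 0.5 SD, 25% at 0.8, 36% at 1.0, 67% at 1.5. It reaches 80% at about 1.75 SD.

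**Step 2. The group-by-time test if all three groups entered.** Suppose both SCI groups drift by d and the healthy group does not.
- Noncentrality: λ = (13 × 5/18) × d² = 3.611 d², so 0.903 at d = 0.5 and 3.611 at d = 1.0.
- Interaction degrees of freedom: (3 − 1)(3 − 1) = 4 and (18 − 3)(3 − 1) = 30.
- Rejection from the noncentral F(4, 30): 9.2% and 25.2%.
- Simulation (20,000 runs per setting; correlations 0.5, 0.8, 0.9): 9.1–9.6% and 25.0–25.8%. Exp versus 1st Con stayed at 4.8–5.3%.
- A separate simulation (8,000 runs, correlation 0.7): 26% at d = 1.0, with Exp versus 1st Con at about 5%.

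If only the two SCI groups entered, the interaction does compare their patterns of change, and this inflation disappears. The contrast would still need to be named and estimated.

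**Step 3. What naming the contrast does not cure.** If the two SCI groups would have changed by amounts 0.5 (1.0) SD apart for reasons other than the programme, the contrast is itself significant in 13% (36%) of trials. These are the step 1 figures, because the test cannot tell a selected difference from a caused one.

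**Step 4. Baseline adjustment.** With a baseline gap g and correlation r, the baseline-adjusted and change estimates differ by (1 − r) × g. For an assumed g of 0.5 SD of one measurement and r from 0.9 to 0.5, that is 0.05 to 0.25 SD. Both estimates should be visible.

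**The case against.** - **A two-way repeated-measures ANOVA normally contains group-by-time, the usual line for a programme effect.** This stands. A reader might infer that a group main effect, driven by healthy people being stronger, was read as evidence for the programme. The documents do not say which line was used, so that inference is unsupported. The gap is that no line, group set or contrast is identified.
- **The healthy group may not have entered the ANOVA.** This stands. The Protocol does not say that they were measured more than once, and sections 5.6 and 5.8 of the Combined protocol and SAP describe healthy controls as a standard for comparison. Step 2 is therefore conditional. No passage reports a shared drift either.
- **Voluntary joining may mean only volunteering for the study.** The wording allows this, so self-selection into an arm is possible but not established. No baseline values are shown, so an actual imbalance is not shown either. On either reading no random allocation is described.
- **Section 5.9 of the Combined protocol and SAP lists LSD, which can be a pairwise comparison, and a pre-post t-test.** They belong to a survey application and are tied to no groups, so they do not close the gap.
- **The title speaks of feasibility and serial cases.** That signals modest evidence but does not qualify the Summary's conclusion.
- **The contrast presumes that 1st Con did not have the programme.** No passage says what that group received. Methods assigns the programme to Exp, yet also speaks of personalised plans for each participant. This objection stands and shapes the fix.

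**Conclusion.** The point holds in a limited form and should be fixed. The SCI groups are non-randomised, the statistics section does not identify the Exp versus 1st Con difference in change, and the Summary's causal statement goes beyond the design.

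The 9% and 25% false-positive rates rest on an assumed shared drift of 0.5 and 1.0 SD of change, three assessments, and repeated measurement of the healthy group. They illustrate the mechanism and do not estimate what happened in this trial. The half-width of about 1.25 SD of change needs only the group sizes and the usual t-test assumptions.

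A reader might go further and infer that the groups differed at baseline, that the reported effect is a healthy-versus-SCI difference, or that 1st Con was untreated. The documents support none of these.

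**What to change.** 1. For each outcome, report the Exp minus 1st Con difference in baseline-to-6-month change, in absolute units (kg, cm, kg/m²) with its 95% CI, as the estimate for the programme. Label it post hoc if the analysis is already done; the section is written in the past tense and the conclusion already stands. Use the healthy group as a descriptive reference, and keep improvement percentage descriptive.
2. State how the two SCI groups were formed and what 1st Con received. Tabulate baseline strength, anthropometry and ASIA status by SCI group. Add a baseline-adjusted estimate as a sensitivity analysis, and say that it does not remove selection.
3. Reword the conclusion to *change associated with taking part in HBRP in a small non-randomised sample of volunteers*.

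**Cost.** No new strength or anthropometric measurements: one contrast with its interval per outcome, one table, one sensitivity result and some text. The price is a visibly wide interval, 80% power only for a difference of about 1.75 SD, a weaker headline, and possibly two estimates that differ. Multiplicity across outcomes remains, so the per-outcome results should be read as exploratory.

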3. RESEARCH TOPIC

"Traumatic Spinal Cord Injury Community Survey Comprehensive Study in North, West and Kurdistan Region of Iraq"

Click or tap here to enter text

3.2 The Research Question:

How many numbers of individuals who infected with traumatic SCI according to assess (levels, causes, and type of therapy), and what are the side effects of injury from a psychological and social point of view?

3.2: Write down the smart research question.

3.3 Research Background (with references in Vancouver style):

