4.3 The resources needed from the institution selected to implement the research?

The resource needed tick		Amount and types		
Laboratory sample (Blood, urine,)		Click or tap here to enter text.		
Devices, instrument, tools		Click or tap here to enter text.		
Patients' or firm's records		Private and Government clinic and hospital and centers of physiotherapy and rehabilitation		
Persons (patients, employers)		Approximately about 100-150 patients and about 10-25 employers		
Others specified	\boxtimes	The experiment will be carried out with physical and functional tests, mostly in the patient's home	79	

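### The protocol does not name the comparison that tests the programme, and it concludes benefit from an 8 v 5 comparison of SCI groups with no allocation method described

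*Protocol*

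**What the plan says.** Four places in the Protocol bear on this.

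- **Methods, design.** "This voluntary controlled trial included 18 volunteers split into three groups". Thirteen have SCI and five are healthy. Of the thirteen: "They joined voluntarily into Two groups, eight in the experimental group (Exp.) and Five in the first control (1st Con". No randomisation or other assignment rule is described in the supplied text.
- **Methods, follow-up.** The programme runs for 6 months, with "regular assessments every 3 months".
- **Statistic Analyze.** "The study used Two-way ANOVA repeated measures as a statistical analysis method, with effect size and improvement percentage (IP) as measures". The alpha is 0.05. No pair of groups, time contrast or interaction term is identified as the test of the programme.
- **Summary, Conclusions.** "The study concluded that HBRP affected positively the muscles morphologically and functionally", despite the long interruption of rehabilitation.

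The combined protocol and SAP does not fill the gap. Its control group (5.6) is healthy people only. Its statistics section (5.9) lists a pre-post t-test, correlations and LSD without saying which groups are compared.

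**The concern.** The conclusion says that the programme caused the improvement. Only one between-group comparison in this design can bear on that: experimental (8) versus first control (5), both with SCI. A comparison with healthy people mixes the programme with everything else that differs between people with and without SCI. A within-group percentage improvement has no comparator at all.

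The named method yields several tests, and the plan does not say which one answers the study question. If the healthy group is one level of the group factor, the group-by-time test asks whether any of the three groups changes differently from the others. Two SCI groups that improve equally, alongside a healthy group that stays put, can make that test significant although the programme added nothing.

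Even the right comparison has two limits here. It rests on 8 and 5 people, and it cannot separate the programme from how people came to be in each group.

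**Working it through.** **Inputs from the documents.** Group sizes 8, 5 and 5 (8 + 5 = 13; 13 + 5 = 18, as stated). Alpha 0.05, taken as two-sided. Assessments at baseline, 3 and 6 months give three time points, or two if only baseline and 6 months are analysed.

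**Assumptions, not in the documents.** Equal SD of change in all groups, set to 1; compound symmetry; linear change over 6 months; the healthy group measured at each time and unchanged; and the sizes of the SCI gains. The plan gives no SD, target effect or power, so there is no stated figure to reproduce.

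**Precision of experimental versus first control**

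SE = √(1/8 + 1/5) = √0.325 = 0.570 SD of change.

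Half-width = t(0.975, df) × 0.570:

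| Analysis | df | t | Half-width (SD) |
|---|---|---|---|
| Two SCI groups, two times | 11 | 2.201 | 1.255 |
| Error pooled over three groups, two times | 15 | 2.131 | 1.215 |
| Error pooled over three groups, three times | 30 | 2.042 | 1.164 |

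In units of the estimated SD, an observed difference must reach about 1.2 to be significant. On the true-SD scale the threshold varies from sample to sample.

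**Group-by-time test when the programme adds nothing**

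Let both SCI groups gain d and the healthy group gain 0. The overall mean gain is 13d/18, so the noncentrality is

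13(d − 13d/18)² + 5(13d/18)² = (13 × 5/18)d² = 3.61d².

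Under the linear-change and compound-symmetry assumptions the same value applies with two times, F(2,15), and with three, F(4,30).

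| d (SD of change) | Noncentrality | Significant, three times | Significant, two times |
|---|---|---|---|
| 0.3 | 0.33 | 6% | 7% |
| 0.5 | 0.90 | 9% | 11% |
| 1.0 | 3.61 | 25% | 32% |
| 1.5 | 8.13 | 54% | 63% |
| 2.0 | 14.44 | 81% | 88% |

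Simulation of the three-time test (40,000 runs) gave 5.0% with no change in any group, 53.6% at d = 1.5 and 81.5% at d = 2.0. In a separate two-time simulation with equal SCI gains, the direct experimental versus first control test stayed at about 5% for every d tried, from 0 to 2.0.

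**The case against.** The strongest reply is that the harm depends on facts the protocol does not state. Methods says the healthy group was tested at college but not how often. If it was tested once, it cannot enter a group-by-time test. Nor does the protocol say that its conclusion rests on that test. This stands, so the table is conditional. At small shared gains (0.3 to 0.5 SD) the rejection rate is only modestly above 5%, and nothing in the documents says how large a gain to expect without the programme.

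It can also be said that an ANOVA or LSD procedure may include experimental versus first control. It may, but neither document says so.

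Three stronger readings are tempting and are not supported.

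- *The study is too small, or falls short of a planned size.* The title frames it as a feasibility study and "Serial Cases Study on ISIS War Survivors in Iraq", for which a missing power calculation is weak criticism. The larger patient numbers stand in a form whose topic is "Traumatic Spinal Cord Injury Community Survey Comprehensive Study". That form does also say "The experiment will be carried out with physical and functional tests, mostly in the patient's home", but it does not tie its numbers to this trial.
- *Each SCI participant chose a group.* That is the natural reading of joining voluntarily into two groups, but the wording could mean only that they volunteered, and the preceding sentence speaks of volunteers being split. Who made the split is not stated.
- *The published benefit is false.* The documents give no results, so this cannot be judged.

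**Conclusion.** The concern holds in a limited form. The plan does not identify the comparison that tests the programme, and its conclusion claims more than the described design can support. Those two statements rest on the text alone.

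The size rests on assumptions. If the healthy group was measured repeatedly and is in the ANOVA, the chance of a significant group-by-time test with no programme effect runs from about 6% to 81% with three time points, and from 7% to 88% with two, as the shared SCI gain goes from 0.3 to 2.0 SD of change. The relevant contrast has a 95% CI half-width of about 1.2 to 1.25 estimated SDs, so even a clear result would be imprecise. With no allocation method described, it could also reflect how the groups were formed. The finding is limited to the supplied text.

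**What to change.** All three changes are to the Protocol.

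1. **Statistic Analyze.** For each outcome, name the experimental versus first control difference in change from baseline to 6 months as the test of the programme. Run it either as a planned contrast in the three-group model or in the two SCI groups alone. Report it with its 95% CI, and use the healthy group only as a reference.
2. **Methods.** Describe the study as non-randomised, and state how SCI participants came to be in each group.
3. **Summary, Conclusions.** Replace the claim of a positive effect with the observed between-group difference and its CI. Add that a programme effect cannot be separated from how the groups were formed.

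**Cost.** No new participants or measurements are needed, but one contrast must be run for each outcome (weight, BMI, each circumference, each strength test). The stated conclusion becomes weaker. If the healthy group is left out of the error term, the two-time half-width widens from 1.21 to 1.25 SD. Keeping it in avoids this loss but relies on equal variances across the SCI and healthy groups.

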## **Background**

Spinal Cord Injury (SCI) is a complex pathology that requires skills in assessment, treatment, and rehabilitation, SCI is a large topic area. Approximately (90%) of SCI cases occur as a result of traumatic causes Globally, incidence varies from 40 to 80 cases per million population. So, people with injuries consequences are becoming more frequent due to conflicts and wars. In Iraq, the main reasons for the occurrence of this injury due to were the Islamic State in Iraq and Syria (ISIS) war, which is resulting in enormous unmet rehabilitation needs. Alarcon Cieza found in his study Rehabilitation the health strategy of the 21st Century that the rehabilitation stakeholders need to bring

together the distinct portraits of rehabilitation under the concept of functioning because much of these unmet needs are concentrated amongst the poorest populations in low-and middle-income countries and conflict-affected settings, which are often ill-equipped to cope with these increasing needs for rehabilitation services. Iraq is regarded as one of these countries its health sectors, including rehabilitation, have been exhausted due to wars and armed violence. However, rehabilitation can be effective across almost all conditions, therefore in some ways, we should have been so backwards about recognizing the effectiveness of rehabilitation for many years.

It is worth noting that healthcare problems are among the most complex problems faced by human beings, especially under conditions of war, armed conflicts, terrorist operations and post-war secretions. In low-middle income countries, so many people would die from SCI within a year, two years, or three years from infection, renal failure, and so on, and also people could not work, and they either were at home or in residential care, just waiting to die. One of the defining characteristics of rehabilitation is that there are many interventions; in contrast to most medical conditions, rehabilitation can take place in any setting as a process for problem-solving.

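### Bed sores and renal infections are answered with psychological support and never counted, so the outcomes cannot show whether the home programme came with more or fewer complications

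*Protocol*

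**What the plan says.** Three parts of the Protocol bear on this point.

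- **Response to complications (Methods).** "To address complex complications like bed sores, renal infections, and muscle atrophy, the authors followed the method of psychological support". The next sentence gives its content: "This method aimed to stimulate patients, willpower, encouraging them to overcome complications". A WhatsApp group showing successful cases is part of the method.
- **Updating and delivery (Methods).** "The authors updated the exercises based on regular assessments every 3 months, tracking muscle strength and endurance". On volume: "The program included five weekly sessions of (45-120) minutes, gradually increasing in intensity". On rest: "Rest periods were personalized based on injury severity and overall health". On coordination: "The authors created a contact link for coordination among medical, rehabilitative teams, and participants, families, overcoming some challenges within the Iraqi healthcare system".
- **Hazard and rationale (Background).** Of low- and middle-income countries, the Protocol says that "so many people would die from SCI within a year, two years, or three years from infection, renal failure, and so on", and elsewhere in the same section it places Iraq among such countries. It also argues for home rehabilitation as a way to prevent the complications of neglect, and says that complex health problems were a major concern seen in the study's own participants.

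The outcomes named in the study questions and Methods are weight, BMI, body-part circumferences and muscle strength, with an ASIA examination. The Statistic Analyze section adds only the method: "The study used Two-way ANOVA repeated measures as a statistical analysis method", with effect size and improvement percentage. No complication appears among the outcomes or in the analysis.

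**The concern.** The Protocol treats complications as a serious hazard and as a reason for the programme, but its only stated response to bed sores and renal infections is motivational, and it does not count them. Two things are at stake.

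The first is participant safety. The reader cannot tell from the text how a complication was detected, who assessed it, or whether it affected what the participant did next.

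The second is the answer the study gives. The title asks about feasibility, and the Summary concludes that the programme acted favourably on muscle. A programme that raised strength while complications became more frequent would give the same favourable result on every planned measure. So would a programme that reduced complications, and a real benefit would then go unreported.

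**Working it through.** The Protocol gives no figure to reproduce here, so the main check sets the passages side by side.

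1. **Is psychological support the stated response?** Yes. Methods says so directly for bed sores, renal infections and muscle atrophy. Atrophy is at least indirectly visible in the strength and circumference measures. Bed sores and renal infections are not visible in any planned measure.

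2. **Does a complication enter the exercise update?** Not in the available text. The update sentence names strength and endurance. Overall health is mentioned for rest periods only.

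3. **Is a complication tied to the medical teams?** The contact link includes them, but no complication, trigger or action is attached to it.

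4. **Are complications counted anywhere?** Not for the home programme. Sections 3.3 and 3.5 of the Combined protocol and SAP list the occurrence of SHCs (not expanded there) as an outcome of a community survey, with no link to the home programme. Section 5.9 of that document plans no complication count.

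5. **Does the Background make this matter?** Yes. It names infection and renal failure as causes of death in such settings, and it makes preventing complications part of the rationale.

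**Exposure, for context.** Five sessions of 45 to 120 minutes give 5 × 45 = 225 to 5 × 120 = 600 minutes a week. Assuming 13 weeks in three months, 5 × 13 = 65 sessions fall between scheduled assessments: 65 × 45 / 60 = about 49 hours to 65 × 120 / 60 = 130 hours. The documents link no complication risk to these hours. They show only how much activity passes between planned assessments.

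**What counts could show.** With zero events in n participants, the exact one-sided 95% upper limit on the risk is 1 − 0.05^(1/n).

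- Exp., n = 8: 1 − 0.05^(1/8) = 1 − 0.688 = 0.312, or 31%.
- 1st Con., n = 5: 1 − 0.05^(1/5) = 1 − 0.549 = 0.451, or 45%.

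These are best-case bounds, and they require that complications were looked for in everyone.

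**The case against.** The strongest reply is that the Methods section is a narrative in the past tense, not an algorithm. It does not say that only strength and endurance were considered. Individual plans were built from interviews about physical, psychological and social well-being, rest followed overall health, weight and BMI were monitored, and medical teams were on the contact link. The sentence on psychological support comes straight after the one on that link and may describe motivation added to ordinary care. The Background sentence on mortality is general and speaks of the first one to three years, whereas these participants were 53.4 to 55 months from injury.

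Much of this stands, and it rules out some stronger readings that a reader might infer:

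- *That a participant with a bed sore or renal infection was simply moved up the programme, or had no medical care.* The documents do not say this. It would be an inference from silence, and the contact link and adapted rest count against it.
- *That the exercise was unsupervised.* The text says home-based and does not describe the level of supervision.
- *That the Background and Methods formally contradict each other.* They are in tension: a named hazard on one side, and on the other a stated response that does not mention assessing or recording it.
- *That the conclusion about muscle is wrong.* Unrecorded complications would not make it false. They leave safety and feasibility unanswered.

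The reply does not supply a record. Baseline interviews cannot capture what arises over six months, and the Background's remark about complex health problems concerns these participants, not only the wider population. It is also fair to say that counts from 8 and 5 people would be weak evidence, but that does not justify having none.

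**Conclusion.** The point holds as a gap in the account of how complications were handled and in their recording. In the available text, psychological support is the only stated response to bed sores and renal infections, the exercise update names only strength and endurance, and no complication is an outcome of the home programme. The measured outcomes therefore cannot show whether the programme was accompanied by more or fewer complications.

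The effect on the results cannot be given a size, because no counts exist to work from. The limits of 31% and 45% show the most that zero events could have established. Because participants joined the two SCI groups voluntarily, a difference in counts would describe the groups and would not by itself show that the programme caused or prevented complications.

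The conclusion rests on the text available for review, parts of which were removed, so absence is claimed only for what can be read. The point deserves action, but it is not a finding that any participant was mismanaged.

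**What to change.** 1. **Reconcile the text.** Bring the Background (hazard and rationale) and Methods (response, update, contact link) into agreement. State how complications were detected and handled, what part the medical team on the contact link had, and whether any complication altered the programme or a participant's attendance. The clinical content is for the study's medical team; this review proposes no rule.

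2. **Record complications.** Ask about bed sores, renal infections and other complications with the same questions in Exp. (n = 8) and 1st Con. (n = 5) at the 3-month assessments. Using the same questions at the same times matters because the Exp. group has far more contact with the study and could otherwise appear to have more complications merely through closer observation. This assumes that 1st Con. attends those assessments, which the Protocol should confirm.

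3. **Report them.** Give counts by group beside the strength results, with exact limits, and without a significance test being taken as evidence of safety.

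4. **If the study is already complete,** as the past tense and the stated conclusions suggest, report whatever was recorded or state that nothing was collected. Then limit the feasibility conclusion to what was measured.

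The cost is some protocol wording and a little more record-keeping. The counts will be imprecise, and the report should say so.
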